14.2 Clinical Laboratory Variables

Clinical laboratory assessments are performed at Screening Visit 1, Baseline (Study Week 0), Study Week 5, and Study Week 10/Early termination.

- Clinical chemistry serum tests include the following:
 - Sodium (Na), potassium (K), chloride (Cl), phosphorus (P), calcium (Ca), carbon dioxide (CO₂), blood urea nitrogen (BUN), creatinine (CR), uric acid
 - Alanine aminotransferase (ALT/SGPT), aspartate aminotransferase (AST/SGOT), gamma-glutamyl transpeptidase (GGT), alkaline phosphatase (ALP), total bilirubin (TBIL), lactate dehydrogenase (LDH)
 - HbA1c (Screening only)
 - Glucose
 - Albumin (ALB), total protein
 - Prolactin
 - Creatine kinase (CK)/creatinine phosphokinase (CPK)
 - Lipid panel
 - Total cholesterol, HDL-cholesterol, triglycerides, LDL-cholesterol, Cholesterol/HDL ratio, Non-HDL cholesterol
- Hematology tests include the following:

- Complete blood count (CBC) including:
 - White blood cell (WBC) count
 - Complete differential (relative and absolute)
 - Hematocrit (Hct), hemoglobin, red blood cells (RBC), platelets
 - Reticulocyte count
- Urinalysis tests include the following:
 - Blood, RBCs, WBCs, protein, glucose, ketones, specific gravity, pH

Clinical laboratory values (in Système International [SI] units) and the change from Baseline values will be summarized by treatment group at each post-Baseline visit using descriptive statistics. The overall minimum and maximum post-Baseline observed and change from Baseline values will also be summarized. For hemoglobin, hematocrit and uric acid, the above summaries will be presented for each gender as well as for both genders combined. For urinalysis with categorical results, the number and percentage of subjects will be tabulated by category at Baseline, Study Week 5 and Study Week 10, and the denominator is the number of subjects with non-missing values for the given parameter, visit and treatment group.

Laboratory values will also be summarized in shift tables by treatment group, to determine the number and percentage of subjects with values classified as below, within, and above normal ranges at each post-Baseline visit relative to the same classification at the Baseline visit. For the by-visit shift summary, the denominator is the number of subjects with non-missing values at Baseline and the given visit for the given parameter and treatment group. For the shift to the overall post-Baseline minimum or maximum, all post-Baseline values will be considered, including unscheduled and out of window values and the denominator is the number of subjects with non-missing Baseline value and at least 1 post-Baseline value for the given parameter and treatment group. For hemoglobin, hematocrit and uric acid, the shift summaries will be presented for each gender as well as for both genders combined.

Clinical laboratory values are potentially clinically important (PCI) if they meet either the low or high PCI criteria listed in Tables 4 and 5. The number and percentage of subjects with post-Baseline PCI values for each of the categories in Table 4 and 5 will be summarized by treatment group for selected parameters. For the overall post-Baseline summaries of PCI values, all post-Baseline values will be considered, including unscheduled and out of window values. Subjects with multiple PCI values for a given parameter will be counted only once for that parameter. For the overall post-Baseline summary, the numerator of the percentage is the number of subjects with at least 1 post-Baseline PCI laboratory value for the given parameter and treatment group, and the denominator is the number of subjects with at least 1 post-

Statistical Analysis Plan
2018

21 August

Baseline laboratory value for the given parameter and treatment group. For hemoglobin, hematocrit and uric acid, the count and percentage of subjects with PCI values will be presented for each gender as well as for both genders combined. Subjects with PCI values will be presented in an additional listing.

Table 4 Criteria for Potentially Clinically Important Laboratory Values – Hematology and Chemistry

Analyte	Conventional Unit	Low PCI Criteria	High PCI Criteria	SI Unit	Low PCI Criteria	High PCI Criteria
Hematology (whole blood)						
Hemoglobin (male)	g/dL	<11	>18	g/L	<110	>180
Hemoglobin (female)	g/dL	<10	>17	g/L	<100	>170
Hematocrit (male)	%	<30	>55	L/L	<0.3	>0.55
Hematocrit (female)	%	<30	>50	L/L	<0.3	>0.5
Leukocyte (White Blood Cell Count)	x 10 ³ /uL	≤2.8	≥15	x 10 ⁹ /L	≤2.8	≥15
Neutrophils	x 10 ³ /uL	≤1.5	No upper limit	x 10 ⁹ /L	≤1.5	No upper limit
Platelet Count	x 10 ³ /uL	≤75	≥700	10 ⁹ /L	≤75	≥700
Chemistry (serum or plasma)						
ALT (SGPT)	U/L	No lower limit	≥3 X ULN	U/L	No lower limit	≥3 X ULN
AST (SGOT)	U/L	No lower limit	≥3 X ULN	U/L	No lower limit	≥3 X ULN
Total Bilirubin	mg/dL	No lower limit	≥1.5 ULN	umol/L	No lower limit	≥1.5 ULN
BUN	mg/dL	No lower limit	≥30.0	mmol/L	No lower limit	≥10.71
Creatine Kinase (CK)	U/L	No lower limit	≥3 ULN	U/L	No lower limit	≥3 ULN
Sodium	mEq/L	≤125	≥155	mmol/L	≤125	≥155
Potassium	mEq/L	≤3.0	≥5.5	mmol/L	≤3.0	≥5.5
Calcium, total	mg/dL	<8.0	>11.0	mmol/L	<2.0	>2.75
Lactate Dehydrogenase (LDH)	U/L	No lower limit	≥3 X ULN	U/L	No lower limit	≥3 X ULN
Alkaline Phosphatase	U/L	No lower limit	≥3 X ULN	U/L	No lower limit	≥3 X ULN
Uric acid (male)	mg/dL	No lower limit	≥10.5	umol/L	No lower limit	≥624.75
Uric acid (female)	mg/dL	No lower limit	≥8.5	umol/L	No lower limit	≥505.75
Albumin	g/dL	≤2.6	≥6.0	g/L	≤26	≥60

Analyte	Conventional Unit	Low PCI Criteria	High PCI Criteria	SI Unit	Low PCI Criteria	High PCI Criteria
Total Protein	g/dL	≤5.0	≥10.0	g/L	≤50	≥100
Chloride	mEq/L	≤85	≥120	mmol/L	≤85	≥120
Glucose (random)	mg/dL	≤45.1	≥200.0	mmol/L	≤2.48	≥11
Serum Creatinine	mg/dL	Not Applicable	>1.5 ULN	umol/L	Not Applicable	>1.5 ULN
Triglycerides	mg/dL	Not Applicable	>300	mmol/L	Not Applicable	>3.39
Gamma-Glutamyl Transferase (GGT)	U/L	Not Applicable	≥3 ULN	U/L	Not Applicable	≥3 ULN

Table 5 Criteria for Potentially Clinically Important Laboratory Values - Urinalysis

Urinalysis (qualitative dipstick)	Low PCI Criteria	High PCI Criteria
Blood (Occult Blood)	Not Applicable	≥+2
Protein	Not Applicable	≥+2
Glucose	Not Applicable	≥+2

Clinical laboratory data will be displayed in data listings with date and study day of collection. All units will be displayed according to SI conventions for units. Out of range values will be flagged in the data listings (i.e., ‘L’ or ‘H’). A separate listing will be provided for a subset of the chemistry, hematology, and urinalysis analytes with values classified as PCI.

The pregnancy results (positive or negative) for female subjects will be presented in a listing.

14.3 Vital Signs

Vital signs including weight and the derived BMI will be collected throughout the study at every visit. Observed vital signs and the changes from Baseline at each post-Baseline visit will be summarized by treatment group using descriptive statistics.

Vital sign values will be considered PCI if they meet the criteria listed in Table 6. The number and percentage of subjects with post-Baseline vital signs that are PCI will be summarized by treatment group at each post-Baseline visit and for overall post-Baseline. For the overall post-Baseline summaries, all post-Baseline values will be considered, including unscheduled and out of window values. Subjects with multiple PCI values for a given parameter will be counted only once for that parameter. For the by-visit summary, the numerator for the percentage is the number of subjects with a post-Baseline PCI vital sign for the given parameter, visit and treatment group, and the denominator is the number of subjects with non-missing values for the given parameter, visit and treatment group. For the overall post-

Statistical Analysis Plan
2018

21 August

Baseline summary, the numerator for the percentage is the number of subjects with at least 1 post-Baseline PCI vital sign for the given parameter and treatment group, and the denominator is the number of subjects with at least 1 post-Baseline vital sign for the given parameter and treatment group. A listing of subjects with any PCI value will be provided.

Table 6 Criteria for Potentially Clinically Important (PCI) Vital Signs

Vital Sign Parameter	Unit	Criteria			
		Observed Value	And/Or	Change Relative to Baseline	Change from Supine to Standing
Systolic blood pressure (supine or sitting)	mmHg	≥180	And	Increase of ≥20	-
		≤90	And	Decrease of ≥20	-
Diastolic blood pressure (supine or sitting)	mmHg	≥105	And	Increase of ≥15	-
		≤50	And	Decrease of ≥15	-
Pulse (supine or sitting)	bpm	≥120	And	Increase of ≥15	-
		≤50	And	Decrease of ≥15	-
Weight	kg	Not Applicable		Increase of ≥7%	-
				Decrease of ≥7%	-

14.4 Electrocardiogram (ECG)

12-lead ECGs are collected at Screening Visit 1, Baseline (Study Week 0), Study Week 1, Study Week 5, Study Week 6, and Study Week 10/Early termination. Observed values of ECG variables (e.g., heart rate, PR interval, QRS interval, QT interval, and QTc interval) and the changes from Baseline at each assessment time point will be summarized by treatment group.

QTcF will also be categorized into the following categories (msec) and the number and percentage of subjects in each category will be summarized by treatment group at each visit and for the overall post-Baseline maximum:

- Observed: ≤450, 451 - ≤480, 481 - ≤500, and >500; >450; >480.
- Change from Baseline: ≤10, 11 – 30, 31 – 60, and >60; >30.

Statistical Analysis Plan
2018

21 August

Electrocardiogram variable values will be considered PCI if they meet the criteria listed in Table 7. The number and percentage of subjects with post-baseline PCI values will be summarized by treatment group at each post-Baseline visit and for overall post-Baseline. For the by-visit summary, the numerator for the percentage is the number of subjects with a post-Baseline PCI ECG for the given parameter, visit and treatment group, and the denominator is the number of subjects with non-missing values for the given parameter, visit and treatment group. For the overall post-Baseline summary, the numerator for the percentage is the number of subjects with at least 1 post-Baseline PCI ECG for the given parameter and treatment group, and the denominator is the number of subjects with at least 1 post-Baseline ECG value for the given parameter and treatment group. A listing of all subjects with any PCI value will be provided.

Table 7 Criteria for Potentially Clinically Important ECG Values

ECG Parameter	Unit	High PCI Criteria
QRS Interval	msec	≥120
PR Interval	msec	≥220
QTcB or QTcF	msec	>500
QTcB or QTcF: change from baseline		>60 msec

14.5 Physical Examination

Physical examinations are performed at Screening Visit 1, Baseline (Study Week 0), Study Week 5, and Study Week 10. Physical examination results (normal, abnormal, and not done) will be summarized in a frequency table by treatment group, body system and visit.

14.6 Other Safety Endpoints

Unless otherwise specified, scores derived based on sub-scores for the safety endpoints in this section will be considered missing if any corresponding sub-scores are missing. No imputations will be performed. Summary statistics for all safety questionnaire data discussed in this section will also be provided by treatment group in Stage 2 for SAS2 from Baseline (Study Week 0) to Study Week 5.

Columbia-Suicide Severity Rating Scale (C-SSRS)

The C-SSRS Baseline/Screening version will be completed at the Screening visit and the version assessing information since the last visit will be completed at all following visits (including the Baseline visit).

Statistical Analysis Plan
2018

21 August

There are 5 questions about suicidal ideation, representing 5 types of suicidal ideation: wish to be dead; non-specific active suicidal thoughts; active suicidal ideation with any methods (not plan) without intent to act; active suicidal ideation with some intent to act, without specific plan; active suicidal ideation with specific plan and intent. If a subject answers “yes” to any of these 5 questions at any post-Baseline visit including unscheduled and out of window visits, this subject will be counted as having suicidal ideation in this study.

There are 5 questions about suicidal behavior, representing 5 types of suicidal behavior: actual attempt; interrupted attempt; aborted attempt; preparatory acts or behavior; suicide. If a subject answers “yes” to any of these 5 questions at any post-Baseline visit including unscheduled and out of window visits, this subject will be counted as having suicidal behavior in this study.

Suicidality is defined as a subject who reported at least 1 occurrence of suicidal ideation or at least 1 occurrence of suicidal behavior at any post-Baseline visit including unscheduled and out of window visits.

All data will be listed. The event counts and the number and percentage of subjects reporting any post-Baseline suicidal ideation, suicidal behavior, or suicidality will be summarized by treatment group for SAS1 over Stage 1 (5 weeks), SAS2 over Stage 2 (5 weeks), and the subjects in SAS1 who were not randomized to the pimavanserin group in Stage 2 over the whole study (10 weeks).

Abnormal Involuntary Movement Scale (AIMS)

The AIMS is a rating scale that was designed in the 1970s to measure involuntary movements known as tardive dyskinesia. The AIMS has a total of 12 items rating involuntary movements of various areas of the patient's body. These items are rated on a 5-point scale of severity. The scale is rated from 0 (none), 1 (minimal), 2 (mild), 3 (moderate), 4 (severe). Two of the 12 items refer to dental care. The remaining 10 items refer to body movements themselves. Total AIMS scores range from 0 to 42.

Observed total AIMS score and the changes from Baseline at each post-Baseline visit will be summarized by treatment group using descriptive statistics.

The number and percentage of subjects with dyskinesia will be summarized by treatment group at each visit and for overall post-Baseline for SAS1 over Stage 1 (5 weeks), SAS2 over Stage 2 (5 weeks), the subjects in SAS1 who were not randomized to the pimavanserin group in Stage 2 over the whole study (10 weeks), and SAS2 over Stage 1 (5 weeks). Dyskinesia is defined as having a score of 3 or more on any of the first 7 AIMS items or a score of 2 or more on any two of the first 7 AIMS items. The tabulations will be presented for subjects who have at least 1 AIMS assessment as well as for a subset of these subjects who do not have dyskinesia at Baseline.

Statistical Analysis Plan
2018

21 August

The individual item scores will be listed but not summarized.

Barnes Akathisia Scale (BARS)

The BARS is a clinician-rated scale to assess drug-induced akathisia and classify it as absent, mild, moderate, or severe. The BARS consists of items that assess the objective presence and frequency of akathisia, the level of an individual's subjective awareness and distress, and global severity. Objective Akathisia, Subjective Awareness of Restlessness, and Subjective Distress Related to Restlessness are rated on a 4-point scale from 0 – 3 and are summed yielding a total score ranging from 0 to 9. The Global Clinical Assessment of Akathisia uses a 6-point scale ranging from 0 – 5.

Observed total score, the score of Global Clinical Assessment of Akathisia, and the corresponding changes from Baseline at each post-Baseline visit will be summarized by treatment group using descriptive statistics.

The number and percentage of subjects with akathisia will be summarized by treatment group at each visit and for overall post-Baseline for SAS1 over Stage 1 (5 weeks), SAS2 over Stage 2 (5 weeks), the subjects in SAS1 who were not randomized to the pimavanserin group in Stage 2 over the whole study (10 weeks), and SAS2 over Stage 1 (5 weeks). Akathisia is defined as having a Global Clinical Assessment of Akathisia score ≥ 2 . The tabulations will be presented for subjects who have at least 1 BARS assessment as well as for a subset of these subjects who do not have akathisia at Baseline.

The individual item scores will be listed but not summarized. .

Simpson Angus Scale (SAS)

The SAS is composed of 10 items and is used to assess pseudoparkinsonism. The grade of severity of each item is rated using a 5-point scale. Total SAS scores can range from 0-40. Signs assessed include gait, arm-dropping, shoulder shaking, elbow rigidity, wrist rigidity, leg pendulousness, head dropping, glabella tap, tremor, and salivation. .

Observed total SAS score and the changes from Baseline at each post-Baseline visit will be summarized by treatment group using descriptive statistics.

The number and percentage of subjects with Parkinsonism will be summarized by treatment group at each visit and for overall post-Baseline for SAS1 over Stage 1 (5 weeks), SAS2 over Stage 2 (5 weeks), the subjects in SAS1 who were not randomized to the pimavanserin group in Stage 2 over the whole study (10 weeks), and SAS2 over Stage 1 (5 weeks). Parkinsonism is defined as having a SAS total score > 3 . The tabulations will be presented for subjects who have at least 1 SAS assessment as well as for a subset of these subjects who do not have Parkinsonism at Baseline.

The individual item scores will be listed but not summarized.

For the overall post-Baseline summaries, all post-Baseline values will be considered, including unscheduled and out of window values.

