 13. Is not actively suicidal (including, on the Columbia Suicide Severity Rating Scale [C-SSRS], an answer of “no” to question 4 or 5 [current or over the last 6 months]) and has not attempted suicide in the 2 years prior to Screening.
 14. If the subject is a female, she must be of non-childbearing potential (defined as either surgically sterilized or at least 1 year postmenopausal) OR must agree to use TWO clinically acceptable methods of contraception throughout the study and for 1 month following study completion. Clinically acceptable methods of contraception include oral, injectable, transdermal, or implantable contraception, an intrauterine device (IUD), and a condom, diaphragm, cervical cap, or sponge with spermicide. Only one of the two clinically acceptable methods can be a hormonal method.
 15. If the subject is a female of childbearing potential, she must have a negative serum pregnancy test at Screening and a negative urine pregnancy test at Baseline.
 16. Must have a detectable blood level of SSRI/SNRI monotherapy identified at Screening.

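### The C-SSRS ideation and composite suicidality tables ignore Baseline and severity, so they mix persisting entry ideation with new ideation and cannot show worsening

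*SAP*

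**What the plan says.** SAP 14.6 lists five ideation questions and five behavior questions. For a yes to any ideation question, the rule is: "at any post-Baseline visit including unscheduled and out of window visits, this subject will be counted as having suicidal ideation in this study". Behavior is counted separately in the same way. The composite then joins the two: "Suicidality is defined as a subject who reported at least 1 occurrence of suicidal ideation or at least 1 occurrence of suicidal behavior". The planned output is: "The event counts and the number and percentage of subjects reporting any post-Baseline suicidal ideation, suicidal behavior, or suicidality will be summarized by treatment group". It covers SAS1 in Stage 1, SAS2 in Stage 2, and a 10-week set that leaves out subjects re-randomized to pimavanserin. The section also states: "All data will be listed". Protocol 9.4.4.6 asks only for counts and percentages during the study.

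Entry is governed by inclusion criterion 13 (Protocol 4.1). It opens "Is not actively suicidal (including, on the Columbia Suicide Severity Rating Scale" and then names "an answer of “no” to question 4 or 5 [current or over the last 6 months", together with a bar on suicide attempts in the previous 2 years. Questions 1 to 3 are not named.

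Elsewhere in SAP 14.6, the AIMS, BARS and Simpson Angus tables are each repeated in subjects free of the condition at Baseline. The BARS text, for example, reads "as well as for a subset of these subjects who do not have akathisia at Baseline". The C-SSRS gets no such table.

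**The concern.** Some subjects will start with low-level ideation. If it continues, they meet the endpoint without anything having changed on treatment. A subject whose wish to be dead is unchanged counts the same as one who newly reports a plan with intent.

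Two things are lost. New ideation is diluted by a background that was there before the first dose. Worsening among subjects who entered with ideation does not register at all. Protocol 6.3.1 describes the ideation part as a five-level severity scale that can be used to follow clinical worsening; the planned tables reduce it to yes or no. Tolerability against placebo is a stated objective (Protocol 2.2), and for this scale these tables are the only planned between-group summary.

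**Working it through.** **Plan's own figures.** The documents state no rate, prevalence or power for the C-SSRS. The only planning figures needed are the Stage 1 group sizes in Protocol 9.5, which reproduce: 188 × 1/4 = 47 pimavanserin and 188 × 3/4 = 141 placebo.

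**Worsening (no rates needed).** Take a subject at item 1 before dosing who would answer yes again in any case. If the subject stays at item 1, the contribution to the any-ideation count is 1. If the subject moves to item 5, the contribution is still 1. The difference is 0, whatever the rates.

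**Dilution of new ideation (all rates assumed).** Let b be the share with entry ideation, r the probability that it is reported again (equal in both arms), and e the new-onset rate in subjects without it. The planned table shows

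rate = b·r + (1 − b)·e.

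Assume e = 15% on pimavanserin and 5% on placebo, a true ratio of 3.0 and a true difference of 10 points.

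| b | r | Placebo | Pimavanserin | Ratio | Difference |
|---|---|---|---|---|---|
| 10% | 60% | 10.5% | 19.5% | 1.86 | 9 points |
| 10% | 90% | 13.5% | 22.5% | 1.67 | 9 points |
| 20% | 60% | 16.0% | 24.0% | 1.50 | 8 points |
| 20% | 90% | 22.0% | 30.0% | 1.36 | 8 points |
| 30% | 60% | 21.5% | 28.5% | 1.33 | 7 points |
| 30% | 90% | 30.5% | 37.5% | 1.23 | 7 points |
| 40% | 60% | 27.0% | 33.0% | 1.22 | 6 points |
| 40% | 90% | 39.0% | 45.0% | 1.15 | 6 points |

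Example, b = 20% and r = 60%: placebo 0.2 × 0.6 + 0.8 × 0.05 = 0.16; pimavanserin 0.12 + 0.8 × 0.15 = 0.24.

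The b·r term cancels in the difference, which is (1 − b) × 10 points. Restricting to subjects without entry ideation keeps 3.0 and 10 points.

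**Precision, b = 20%.** The expected excess on pimavanserin is the same in both tables: 47 × 0.08 = 3.76, and 47 × 0.8 × 0.10 = 3.76. What changes is the background noise.
- Planned table, r = 60%: SE = √(0.24 × 0.76/47 + 0.16 × 0.84/141) = 0.070, so the difference is 0.08/0.070 ≈ 1.15 SEs. At r = 90% it is 0.08/0.075 ≈ 1.06.
- Ideation-free subset (37.6 and 112.8 expected subjects): SE = √(0.15 × 0.85/37.6 + 0.05 × 0.95/112.8) = 0.062, so 0.10/0.062 ≈ 1.62 SEs.

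**Unequal persistence.** If treatment also relieves existing ideation, the two effects can cancel. With b = 20% and placebo persistence 90%, placebo shows 22%. Solving 0.2·r + 0.8 × 0.15 = 0.22 for pimavanserin gives r = 0.50. At that value the table shows 22% in both arms despite a threefold new-onset ratio.

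**The case against.** **Behavior.** A reader might infer that new suicidality of every kind is hidden. The documents do not support that. Behavior has its own definition and its own row, and every assessment after Screening asks about the time since the previous visit (Protocol 6.3.1), so persisting ideation cannot mask a new act there. This objection stands and limits the point to ideation and the composite.

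**Entry.** A reader might infer that items 1 to 3 are all admitted. Criterion 13 requires that the subject not be actively suicidal, with questions 4 and 5 given as included conditions and not as the only ones. The SAP's names for items 2 and 3 contain the word active. Only item 1 is clearly admissible.

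**Other outputs.** All data are listed. SAP 14.6 also promises questionnaire summaries for SAS2 over Study Weeks 0 to 5 by Stage 2 arm, which shows group history before re-randomization. Recognized worsening may be recorded as an adverse event (Protocol 7.1.1, 7.2.2.1) and tabulated under SAP 14.1. These soften the problem without closing it: a listing is not a group comparison, the SAS2 summary does not track change within a subject, and adverse events are elicited by a nonspecific question (Protocol 7.4.1).

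**Size.** The ratio is the least favorable metric; the difference keeps the fraction 1 − b, and randomization balances the background in expectation. That is correct. It does not touch the loss of worsening.

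**Importance.** It is tempting to add that the measure mainly reflects residual depression, or that the absence of a Data Monitoring Committee (SAP 17) makes this worse. No figure in the documents supports the first. The second confuses an end-of-study table with monitoring during the trial.

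**Conclusion.** The point holds for the ideation row and the composite. Neither refers to Baseline or severity, and no planned group table separates persisting from new or worsened ideation. The blindness to worsening among subjects who would answer yes anyway follows from the definition alone. The dilution depends on rates that the documents do not give. Over 10–40% entry ideation and 60–90% persistence, equal in both arms, a true ratio of 3.0 appears as 1.86 down to 1.15, and the risk difference keeps 90% down to 60% of its size.

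The SAP follows Protocol 9.4.4.6 as written, so this is a gap in the analysis and not a contradiction between the documents. It is also out of line with the SAP's own practice: Baseline-free subsets for the three movement scales, shift tables for laboratory values (14.2) and change criteria for vital signs and QTcF (14.3, 14.4).

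A reader might conclude that the safety judgment should rest on Baseline-referenced tables alone. That goes too far. About 47 subjects receive pimavanserin in Stage 1, and a single since-last-visit assessment is a short reference for ideation that may come and go.

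**What to change.** In SAP 14.6, for SAS1 in Stage 1 and SAS2 in Stage 2, add by treatment group:

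1. New ideation: number and percentage with any post-Baseline yes among subjects with no ideation in the pre-treatment reference period.
2. A shift table of the worst post-Baseline ideation category (0 to 5) against the pre-treatment category, with emergence of items 4–5 shown separately.

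State the reference period. For Stage 1, use the Baseline visit plus the Screening record for the past 6 months. For Stage 2, use Study Week 5, with all of Stage 1 as an alternative because one since-last-visit assessment covers little time.

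Report both beside the existing any-ideation count and interpret all of them descriptively.

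The cost is SAP wording and two more tables per stage from data already collected (Protocol Table 2); visits, assessments and conduct do not change. The drawback is a smaller ideation-free subset: at an assumed 20% entry ideation, about 38 of 47 pimavanserin and 113 of 141 placebo subjects in Stage 1. The longer the reference period, the smaller the subset.
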